Conservative Management Equally Effective to New Suture Anchor Technique for Acute Mallet Finger Deformity: A Prospective Randomized Clinical Trial

Date: May 23th, 2013

The study was designed as a randomized - prospective study and included 29 patients (22 male, 7 female) aged between 17 and 61 years (mean: 36.4 years) who were scheduled for mallet finger treatment between June 2013 and July 2015. All patients who agreed to participate in this study gave their informed consent prior to their inclusion in the study for expected complications and results of the treatment procedure. The patients were included in the study after approval was received from the Ethics Committee (2014/288). Patients were randomized into two groups using closed opaque envelopes. Inclusion criteria were having Webbe–Schneider tip I and II fractures; Webbe–Schneider subtype A and B fractures, ability to provide closed reduction, and voluntariness to participate in the study. Patients with Webbe–Schneider subtype C fractures were excluded from the study because subtype C fractures mostly require surgery, conservative treatment has poor results.

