## **Statistical Analysis**

Quantitative variables are described as means and standard deviations or medians and interquartile range. Fisher's exact or the Mann-Whitney U test (asymmetric distribution) was applied to compare the two groups in relation to the quantitative outcomes. RO M value was analyzed using OpenEpi, a Windows-based software program. The level of significance was set at 5%, where P < 0.05 was considered statistically significant.

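### The title claims equal effectiveness, but the analysis text offers only tests of difference, with no equivalence margin and no confidence interval for the between-group difference

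*Protocol*

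**What the plan says.** The Protocol title states a finding of similarity: "Conservative Management Equally Effective to New Suture Anchor Technique for Acute Mallet Finger Deformity". The study description reports that the trial "included 29 patients (22 male, 7 female") and that "Patients were randomized into two groups using closed opaque envelopes". It gives no group sizes, hypothesis or sample-size reasoning in the text available.

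The SAP's Statistical Analysis section describes variables by mean and SD or by median and interquartile range. Its rule for comparing the groups is "Fisher's exact or the Mann-Whitney U test (asymmetric distribution) was applied to compare the two groups in relation to the quantitative outcomes". Its decision threshold is "The level of significance was set at 5%, where P < 0.05 was considered statistically significant". For ROM, the only outcome it names, it says that the "value was analyzed using OpenEpi, a Windows-based software program".

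The text gives no margin, no interval for the between-group difference, and no statement of how P >= 0.05 is to be read.

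**The concern.** Fisher's exact and Mann-Whitney U both take no difference as the null hypothesis. They can reject equality but cannot demonstrate it. To claim that two treatments are equally effective, one must say how large a difference would still count as equal and then show that larger differences are excluded. The SAP text does neither.

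The ROM sentence does not fill the gap. OpenEpi is a program, so the reader cannot tell whether ROM received a P value, an interval or both. Even an interval would not justify the title without a margin to judge it against.

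At stake is the headline conclusion of a comparison between conservative and surgical treatment. Readers would take the two as interchangeable without knowing what difference the data rule out. If the claim rests on P >= 0.05, true differences of moderate size would often receive the same label.

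**Working it through.** There is no sample-size or power figure to reproduce: 29 is the number of patients included. The logical point needs no arithmetic. The calculations below show how much a non-significant result would leave open.

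**Inputs from the documents:** 29 patients in two randomized groups (Protocol); 5% significance level (SAP).

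**Assumptions:** 14 vs 15 patients (the split is not stated), two-sided testing, and a normal outcome with common SD. Differences are in SD units because no SD is given.

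**1. Interval width.** SE = SD × √(1/14 + 1/15) = 0.3716 SD, with 14 + 15 − 2 = 27 degrees of freedom.
- 95% half-width = t(0.975, 27) × 0.3716 = 0.7625 SD.
- 90% half-width = t(0.95, 27) × 0.3716 = 0.633 SD.

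**2. Chance of P >= 0.05 when a true difference d exists.** The t test uses the non-central t distribution with non-centrality d/0.3716. The exact Mann-Whitney test uses 200,000 simulated normal trials (critical U <= 59, actual level 0.0459; for 12 vs 17, U <= 57).

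| True difference | t test, 14/15 | Mann-Whitney, 14/15 | t test, 12/17 | Mann-Whitney, 12/17 |
|---|---|---|---|---|
| 0.5 SD | 74.6% | 76.9% | 75.1% | 76.8% |
| 0.8 SD | 45.4% | 49.2% | 46.6% | 49.6% |
| 1.0 SD | 26.3% | 29.9% | 27.5% | 30.7% |

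Non-significance is the likelier result at 0.5 SD, about a coin toss at 0.8 SD, and the less likely result at 1.0 SD. A less even split changes little.

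**3. Fisher's exact test.** The SAP attaches this test to quantitative outcomes. It is modelled here for a yes/no outcome, with assumed success rates and full enumeration of the possible results. The range covers which arm has 14 patients.
- 90% vs 60%: P >= 0.05 in 59–65% of trials.
- 90% vs 50%: P >= 0.05 in 39–44% of trials.

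**4. Would a larger trial cure it?** With 100 per arm and a true difference of 0.2 SD, the non-centrality is 0.2/√(2/100) = 1.41, and P >= 0.05 still occurs in 71% of trials. Whether 0.2 SD matters cannot be judged without a margin.

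**5. What a formal equivalence test could achieve with 29 patients.** This uses two one-sided 5% t tests, true difference zero, and 400,000 simulations.

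| Margin | Power |
|---|---|
| 0.5 SD | 0.5% |
| 0.8 SD | 35% |
| 1.0 SD | 67% |
| 1.1 SD | 79% |

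A normal approximation gives slightly higher values (39% at 0.8 SD, 70% at 1.0 SD). The t-based figures are preferable at this sample size.

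**The case against.** The strongest reply is that the record is incomplete. Parts of both documents were not available for this review, so a margin or interval could stand elsewhere. That limit is real, and the point is confined to the text supplied. If such a passage exists, citing it beside the claim would answer much of the concern.

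Second, the link between the title and non-significant tests is inferred. The SAP does not say how P >= 0.05 is read, and no results are given. This stands too, and it makes the error rates conditional. It does not rescue the title, because the text gives no other criterion by which equality could be judged.

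Third, the numbers rest on assumed splits, distributions and success rates. A normal model also sits awkwardly with an SAP that ties Mann-Whitney to asymmetric distributions. The figures are therefore illustrations of scale. The conclusion does not depend on them.

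Fourth, effectiveness may rest on outcomes other than ROM, and no primary outcome appears in the text supplied. ROM is the only outcome named, so it is a reasonable place to start, but any other outcome behind the claim needs the same treatment. The unnamed ROM method, taken alone, would be only a reporting gap.

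**Conclusion.** The concern holds. The claim of equal effectiveness is unsupported by the analysis described, and that follows from the kind of test named, whatever the sample size. Under the stated assumptions, the small sample leaves differences of up to about 0.76 SD either side of the estimate unexcluded at the 95% level. Confidence is high about the supplied text. It cannot extend to parts of the plan that were not available. Because the defect lies in the headline inference, it must be fixed.

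**What to change.** 1. Replace the equality wording in the title, and wherever the conclusion repeats it, with *no statistically significant difference was detected*, if that is the result.
2. Name the ROM analysis method in the SAP. Report the between-group ROM difference with its 95% confidence interval: a Hodges-Lehmann estimate alongside Mann-Whitney, or a mean difference. Use degrees if that is the unit of measurement.
3. State in words the largest ROM difference in each direction that the interval does not exclude. Do the same for any other outcome on which the claim rests.
4. Keep an equivalence claim only if the 90% confidence interval (two one-sided 5% tests) lies wholly inside a clinically justified margin set without reference to the results. Label the margin post hoc if it is set after data collection, which is possible because the study is described in the past tense.

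Steps 1 to 3 cost wording changes and an interval calculation for each outcome concerned, on data already collected, with no new patients. The drawback is a weaker headline. Step 4 is optional and costs more: the margin must be justified, and power with 29 patients is poor unless the margin is wide.

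### Do the protocol's dates undermine its claims of a prospective design and prior ethics approval?

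*Protocol*

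**What the plan says.** The Protocol's date line reads "Date: May 23th, 2013". The design paragraph below it is in the past tense. It says the study "included 29 patients (22 male, 7 female) aged between 17 and 61 years (mean: 36.4 years") and that these were patients "who were scheduled for mallet finger treatment between June 2013 and July 2015". The title already states the finding: "Conservative Management Equally Effective to New Suture Anchor Technique for Acute Mallet Finger Deformity".

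On design, the paragraph says "The study was designed as a randomized - prospective study". On ethics, it says "The patients were included in the study after approval was received from the Ethics Committee (2014/288"). It gives a reference number but no calendar date of approval, and no date on which the first patient was included.

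The SAP's Statistical Analysis section, as supplied, carries no date and no cohort figures. It too is in the past tense: a test "was applied to compare the two groups in relation to the quantitative outcomes".

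**The concern.** Two pairs of statements seem unable to stand together.

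- **Date against content.** A document written on 23 May 2013 could not report how many patients had been treated by July 2015, their mean age, or the result. A reader who trusts the date would take the analysis as settled before any data existed, when the text shows that at least the Protocol wording came later.
- **Approval against enrolment.** If 2014/288 is a year and a serial number, approval came in 2014. Patients treated from June 2013 would then have entered before approval, or been treated first and added afterwards. In the second case they could hardly have been randomised prospectively under the approved plan.

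At stake would be the credit given to the plan as a pre-enrolment document, and the truth of the sentence on ethics approval. That could affect a sizeable share of a 29-patient trial.

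**Working it through.** The documents state no sample size calculation, power or approval date, so there is no figure of the plan's own to reproduce. The cohort arithmetic is sound: 22 + 7 = 29. The rest is calendar arithmetic.

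**Date line against cohort** (inputs: the date line and the treatment window)

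- 23 May 2013 to 1 June 2013, the earliest opening of the window: 9 days.
- 23 May 2013 to 1 July 2015 and to 31 July 2015: 769 and 799 days.

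The final cohort description cannot have been written on the stated date. This needs no assumption.

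**Approval against treatment window** (assumption: 2014 in the reference is the year of approval)

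- Shortest gap, 30 June 2013 to 1 January 2014: 185 days.
- Longest gap, 1 June 2013 to 31 December 2014: 578 days.

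**Patients who might precede approval** (further assumptions: enrolment began at the start of June 2013, and accrual was uniform)

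- June 2013 to July 2015, both months counted: 26 months.
- Approval at the start of 2014, 7 months before it: 29 × 7/26 = 7.8 patients (27%).
- Approval at the end of 2014, 19 months before it: 29 × 19/26 = 21.2 patients (73%).

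**What a post-approval subset would offer**

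- Patients remaining: 29 − 21.2 = 7.8 to 29 − 7.8 = 21.2, or about 8 to 21 across two groups.
- At the lower end, with four per group, there are 70 ways to divide eight patients into two groups of four. The smallest two-sided exact Mann-Whitney P is 2/70 = 0.029, so with no ties only complete separation of the groups would fall below 0.05.

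**What the documents claim, against what the dates disprove**

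- *Prospective design.* The Protocol describes how patients were allocated and followed. Writing that up after July 2015 does not contradict it.
- *Pre-specification.* Neither visible text calls the analyses pre-specified, and neither states a sample size target. The 29 is reported as the number included.
- *SAP.* The dated page is the Protocol. The past tense in the SAP suggests late writing, but does not by itself show that the tests were chosen after the data were seen.

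**The case for a change.** The strongest case for action is that readers use a protocol date to judge whether methods came before data. Here the date says they did and the text says they did not. If 23 May 2013 is the date of an original plan carried forward, this text is still not that plan. The SAP leaves open the choice between means and medians and between tests, and those choices cannot be credited as made in advance on this evidence. Prior approval is a basic claim that a reader cannot confirm from the dates given. Three dates would settle all this at almost no cost.

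Most of that stands as a comment on the record. The date line and the cohort description do conflict, and the sponsor can clear this up from the dated approval letter, the date of first inclusion and the date of this version. If those dates contradict the sentence on approval, the sentence is wrong and should say what happened.

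It does not carry over into the plan. The approval limb rests on two inferences: the year read from a reference number, and an enrolment start read from when treatment was scheduled. Passages were also removed from both documents before review, so a missing version history cannot be held against them. Relabelling the statistical section would withdraw a claim that the visible text does not make. The subset analysis answers no identified source of bias, and an approval gap is a regulatory matter that no reanalysis repairs.

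**Conclusion.** This is a documentation inconsistency, and no change to the plan follows. The Protocol's date cannot be the date on which this wording was written: the gap is at least 769 days, with no assumption needed. The text therefore earns no credit as a plan fixed before enrolment, but that does not show that allocation or follow-up was retrospective.

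The conflict over ethics approval is apparent only. It depends on 2014 being the approval year and on patients having been included from June 2013, and the documents confirm neither. The range of 8 to 21 patients adds uniform accrual to those assumptions. It is illustrative and cannot support a conclusion about how many patients, if any, preceded approval.

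Reconciling the dates would tidy the record but would leave every test, estimate and conclusion as it is. The one analysis that might be added would be small and imprecise, and would not address the approval question.

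### Does a title with no fracture-type limit claim more than the eligibility criteria allow?

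*Protocol*

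**What the plan says.** The Protocol's title states a result: "Conservative Management Equally Effective to New Suture Anchor Technique for Acute Mallet Finger Deformity". Its only limit on the condition is the word acute.

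The paragraph beneath the title describes a randomized study that "included 29 patients (22 male, 7 female"), aged 17 to 61 years, "who were scheduled for mallet finger treatment between June 2013 and July 2015". It then sets the entry criteria. On type: "Inclusion criteria were having Webbe–Schneider tip I and II fractures". On subtype and reducibility: "subtype A and B fractures, ability to provide closed reduction". Willingness to take part is also required. Subtype C fractures were "excluded from the study because subtype C fractures mostly require surgery, conservative treatment has poor results".

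The SAP, under Statistical Analysis, describes summary statistics and two-group tests: "The level of significance was set at 5%, where P < 0.05 was considered statistically significant". It says nothing about the population to which the result applies.

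**The concern.** Two things make the title look like more than an ordinary abbreviation.

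- It is phrased as a finding, not as a neutral description of a comparison. The scope of a stated finding matters more than the scope of a label.
- The Protocol leaves out subtype C because it expects conservative treatment to work poorly there. The title, read alone, extends equal effectiveness to that same group.

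The stake is misapplication. Someone who saw only the title might think conservative management had been shown equal to the suture anchor technique for subtype C fractures, or for fractures that cannot be reduced closed. If the criteria were followed, the trial has no data on either. Injuries without a fracture also seem to fall outside, since the type and subtype criteria are worded in terms of fractures, though no explicit exclusion says so.

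**Working it through.** No formula applies, because the question is one of scope. The check is a comparison of texts, followed by asking what would differ if the title were narrower.

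**Title against criteria**

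| Feature | Title | Eligibility text |
|---|---|---|
| Timing | acute | no separate timing criterion |
| Fracture type | not limited | I and II |
| Subtype | not limited | A and B; C excluded, with a reason |
| Reducibility | not limited | closed reduction must be achievable |

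Three of the four features are narrower in the criteria than in the title, so the literal mismatch is confirmed.

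**Do the two texts contradict each other?** They do not. The remark on subtype C is a reason for leaving that group out. It is not a result, and the Protocol presents no subtype C data. A trial may report on the group it studied and explain why it did not study another.

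**Is a wider source population described?** No. The phrase about patients scheduled for mallet finger treatment refers to the 29 who were included. The reported sex counts agree with that total: 22 + 7 = 29. The text does not say that a broader series was screened and then cut down.

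**Can the excess scope be sized?** The available text gives no number screened, no number excluded and no breakdown of the 29 by type or subtype. Any count of patients covered by the title but not by the data would need an invented exclusion share. Counting type-by-subtype categories would not help either, because categories are not patients.

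**What would a narrower title change?**

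- Patients enrolled: none, because the criteria already apply.
- Randomization: none.
- Outcomes, tests and the 5% level: none.
- The conclusion that the data can support: none. It is bounded by the criteria under either title.

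**The case for a change.** The best argument for acting is that a title worded as a conclusion is the most widely read sentence in the document, and that here it reaches a group for which the authors themselves doubt conservative treatment. Naming the studied population would cost only a longer title.

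Part of this stands. The title is wider than the population, and a report of the trial should state its conclusion for closed-reducible type I and II, subtype A and B fractures. An analyst or author working from this Protocol would do that without instruction, because the criteria are explicit and the subtype C exclusion comes with its reason.

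The rest does not amount to a defect in the plan. The harm requires a reader who takes in the title and skips the single paragraph under it. Most trial titles are wider than their eligibility criteria, and how much detail a title carries is an editorial choice. It would also be wrong to fault the whole plan for never narrowing the claim. Passages of both documents are not available for review, and no conclusion section is among the text at hand.

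The title does raise a weightier question. The available Statistical Analysis text gives significance tests at 5% and no equivalence margin, with 29 patients enrolled. A non-significant difference would not by itself establish equal effectiveness, even among eligible fractures. That is a different point, and adding a fracture type to the title would leave it where it is.

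**Conclusion.** The concern describes the text correctly but calls for no change to the plan. The title is broader than the eligibility criteria on type, subtype and reducibility. The criteria, the exclusion and the reason for it are disclosed immediately below the title. The effect on enrolment, allocation, analysis and the supportable conclusion is nil. The reach of the title beyond the data cannot be quantified from the documents.

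This rests on two assumptions: that the type and subtype criteria were meant to apply together, and that they were followed, so that none of the 29 patients had a subtype C fracture or one that could not be reduced closed. The available text gives no breakdown to confirm the second. If it failed, the issue would be adherence to the criteria and not the wording of the title.

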## **Statistical Analysis**

Quantitative variables are described as means and standard deviations or medians and interquartile range. Fisher's exact or the Mann-Whitney U test (asymmetric distribution) was applied to compare the two groups in relation to the quantitative outcomes. RO M value was analyzed using OpenEpi, a Windows-based software program. The level of significance was set at 5%, where P < 0.05 was considered statistically significant.

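### The SAP names Fisher's exact test for quantitative outcomes and defines no categories: wrong as written, though perhaps only a drafting slip

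*SAP*

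**What the plan says.** All the relevant wording is in the SAP, section Statistical Analysis.

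- Description: "Quantitative variables are described as means and standard deviations or medians and interquartile range".
- Comparison of groups: "Fisher's exact or the Mann-Whitney U test (asymmetric distribution) was applied to compare the two groups in relation to the quantitative outcomes".
- Range of motion: "RO M value was analyzed using OpenEpi, a Windows-based software program". This names a program but no test.
- Threshold: "The level of significance was set at 5%, where P < 0.05 was considered statistically significant". Sidedness is not stated.

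The section names no other test, mentions no categorical outcome and gives no cut-point. The protocol reports 29 patients and says: "Patients were randomized into two groups using closed opaque envelopes". It gives neither the size of each group nor the allocation ratio. Its only categories are the fracture types and subtypes used for eligibility, which are not outcomes.

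**The concern.** Fisher's exact test compares counts in a table. To use it on a quantitative outcome, each patient's value must first be put into a category, and the SAP does not say where the boundaries lie. Two things would follow if the sentence were carried out as it stands:

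- Information is lost. With 29 patients, replacing each value by a position above or below a cut can cost a large share of the power.
- Whether P falls below 0.05 can turn on a cut-point that the reader cannot see.

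On one reading the problem goes further. If the parenthesis about asymmetry reserves Mann-Whitney for skewed data, Fisher's is the only test named for a symmetric quantitative outcome. The descriptive sentence provides for means and standard deviations, so symmetric variables seem to be foreseen.

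The harm is conditional. If Fisher's test was used only on categorical results, no power was lost and only the text needs correcting. As written, a reader cannot tell which case applies to any outcome, ROM included.

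**Working it through.** The supplied text contains no power or sample-size figure, so there is none of the plan's own to reproduce. The defect is established by the wording; the arithmetic below only shows what could be at stake.

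**Inputs from the documents:** 29 patients, two groups, 5% significance level.

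**Assumed, because the documents do not say:** groups of 14 and 15, two-sided testing, a split at the overall median, the distribution and the size of the difference.

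**Step 1: dependence on the cut (exact).** With 29 distinct values, one patient sits on the median. Suppose that patient is in the group of 15. For a fixed total k above the cut, the probability of x in the group of 14 is

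P(x) = C(14, x) × C(15, k − x) / C(29, k),

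and the two-sided P value sums every P(x) no larger than the one observed. C(29, 14) = C(29, 15) = 77,558,760.

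- Strictly above the median: 4/14 versus 10/15, k = 14. Observed term: 1,001 × 3,003 / 77,558,760 = 0.03876. Lower tail (x ≤ 4): 0.00002 + 0.00053 + 0.00641 + 0.03876 = 0.04572. Upper tail (x ≥ 10): 0.01762 + 0.00214 + 0.00012 = 0.01988. P = 0.066.
- At or above the median: 4/14 versus 11/15, k = 15. Observed term: 1,001 × 1,365 / 77,558,760 = 0.01762. Lower tail (x ≤ 4): 0.00012 + 0.00214 + 0.01762 = 0.01988. Upper tail (x ≥ 11): 0.00641 + 0.00053 + 0.00002 = 0.00696. P = 0.027.

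The data are the same, one patient is classified differently, and the results fall on opposite sides of 0.05. The table was chosen to show that this can happen.

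**Step 2: power (simulation).** 20,000 trials per row, normal data, shift in the group of 15, exact Mann-Whitney:

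| Difference (SD) | Mann-Whitney | t-test | Fisher, strictly above | Fisher, at or above | Two splits disagree |
|---|---|---|---|---|---|
| 0 | 4.6% | 4.9% | 2.6% | 2.6% | not tabulated |
| 0.5 | 23.2% | 25.2% | 8.4% | 16.2% | 8.2% |
| 1.0 | 70.2% | 73.8% | 36.3% | 52.9% | 16.5% |
| 1.5 | 96.2% | 97.1% | 74.8% | 86.6% | 11.8% |

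At 1 SD the loss against Mann-Whitney is 70.2 − 36.3 = 33.9 points or 70.2 − 52.9 = 17.3 points. The first row shows no excess of false positives.

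**Step 3: sensitivity at 1 SD.**

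- Shift in the group of 14: the two Fisher values swap (52.7% and 36.3%).
- Groups of 12 and 17, shift in the larger: Mann-Whitney 69.3%, Fisher 31.6% or 51.2%.
- Groups of 10 and 19, shift in the larger: Mann-Whitney 66.6%, Fisher 23.3% or 45.8%.
- The reserved-for-asymmetry reading, modelled as Mann-Whitney when Shapiro-Wilk gives P < 0.05 in either group and Fisher otherwise (14 and 15): 39.2% or 54.4% with normal data. With lognormal data (sigma 0.6) it is 79% to 84%, against about 88% for Mann-Whitney throughout, so the loss is much smaller.

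**The case against.** The strongest reply is that this is a wording slip. No other test is named for categorical results, so Fisher's was probably meant for those, and nothing in the supplied text shows it applied to a quantitative outcome. This stands as a limit on the harm. It does not rescue the sentence, which would still need rewriting.

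Second, the parenthesis may merely explain why a rank test was chosen: the outcomes were asymmetric. The SAP does not say that Mann-Whitney is for asymmetric data only, and the sentence on means and standard deviations concerns description and may cover baseline variables such as age. This also stands. That Fisher's is the only test left for symmetric outcomes is one reading, not a necessary one.

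Third, the power figures rest on assumed inputs, and nothing in the documents points to a median split. This is correct; they are an illustration and the conclusion does not depend on them. The available text is also incomplete, so the point is confined to the SAP section quoted.

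Fourth, naming OpenEpi for ROM is not an error, since the preceding sentence can cover ROM. Agreed. It only leaves open which of the two tests was used.

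A reader might infer something stronger: that ROM or another quantitative outcome was in fact dichotomised, and that the equivalence announced in the protocol's title is a product of lost power. The documents support neither step. They show no cut-point, no result and no outcome matched to a test.

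**Conclusion.** The sentence is wrong as written, with high confidence: it assigns a test for counts to quantitative outcomes and gives no categories. Confidence that Fisher's test was actually run on a quantitative outcome is only low to medium.

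If it was, the loss could be material. Under the assumptions of 14 versus 15, normal data, 1 SD and a median split, power is about 70% with Mann-Whitney and 36% or 53% with Fisher's, and the two ways of placing the median patient disagree on significance in about 17% of trials. Other effect sizes, cuts and distributions give different figures. If it was not, the harm is confined to a misleading text. No inflation of false positives is claimed on either account. The section should be corrected, but the finding does not by itself undermine the trial's conclusions.

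**What to change.** 1. State which test was run on each reported outcome, including ROM.
2. Replace the comparison sentence with: *Categorical outcomes (categories listed) were compared with Fisher's exact test; quantitative outcomes, including ROM, were compared on individual patient values with the Mann-Whitney U test.*
3. Because the SAP is written in the past tense, make that sentence true before adopting it. Rerun any quantitative outcome that was tested with Fisher's exact, label the result as a correction, and show the original P value and cut-point beside it. If there was none, say so; no rerun is then needed for this reason.

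A Hodges-Lehmann difference with a 95% confidence interval would be a useful addition but is optional.

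The cost is one line per outcome, one rewritten sentence and, at most, a rerun on 29 records. Mann-Whitney throughout gives up about 3 to 4 power points against a t-test if the data are truly normal (73.8 − 70.2 = 3.6 at 1 SD). In the lognormal example the advantage is reversed (87.7% against 76.4%).

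### Does leaving fracture subtype A/B out of the randomisation and the analysis weaken the comparison of the two groups?

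*SAP*

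**What the plan says.** The protocol's study paragraph reports that the trial "included 29 patients (22 male, 7 female) aged between 17 and 61 years". Eligibility rests on two parts of one fracture classification: "Inclusion criteria were having Webbe–Schneider tip I and II fractures", and in addition "Webbe–Schneider subtype A and B fractures". Both are therefore known before treatment. Subtype C is left out on the ground that "subtype C fractures mostly require surgery, conservative treatment has poor results". On allocation the protocol says only: "Patients were randomized into two groups using closed opaque envelopes". It names no stratification factor.

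The SAP's Statistical Analysis section offers two-group tests without covariates: Fisher's exact test, or "the Mann-Whitney U test (asymmetric distribution) was applied to compare the two groups in relation to the quantitative outcomes", at the 5% level. It adds that range of motion (ROM) was analysed in OpenEpi, without naming the test used. The available text describes no table of subtype by arm and no subtype-adjusted comparison. It gives no arm sizes, number of A and B patients, standard deviation, target effect or power.

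**The concern.** Subtype is recorded for every patient at entry, and the protocol itself uses subtype to predict how conservative treatment will turn out. One of the two treatments compared is conservative, so subtype is the natural candidate for a prognostic factor. In 29 patients allocated without stratification, the arms can easily differ in their A/B mix by chance. If A and B also differ in prognosis, part of any observed difference between the arms would be due to subtype, and unexplained subtype variation would widen the confidence interval. That would matter for a trial whose title concludes that the treatments are equally effective: such a claim needs comparable arms and a narrow interval. The remedy also seems almost free, namely one table row and one adjusted comparison beside the Mann-Whitney test.

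**Working it through.** The plan gives no power or precision figure to reproduce, so the check asks what the omission costs.

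**Inputs.** From the protocol: 29 patients, two groups, subtypes A and B. From the SAP: Mann-Whitney test, 5% level (two-sided assumed). Assumed, because the documents do not say: arms of 14 and 15; 5 to 14 patients with subtype B; normal outcomes with within-subtype SD 1; treatment effect 1.0 SD; A–B prognosis difference 0, 0.3, 0.5 or 1.0 SD.

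**1. Chance of imbalance.** With b subtype B patients, of whom x fall in the arm of 14, P(x) = C(b,x)·C(29−b,14−x)/C(29,14), and the gap is |x/14 − (b−x)/15|. For b = 12, x = 4 gives |0.286 − 0.533| = 0.248 and x = 8 gives |0.571 − 0.267| = 0.305. A gap of at least 20 points therefore needs x ≤ 4 or x ≥ 8.

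| Subtype B patients | P(gap ≥ 20 points) | P(gap ≥ 30 points) |
|---|---|---|
| 5 | 17% | 4% |
| 9 | 24.5% | 10.9% |
| 12 | 26.4% | 13.9% |
| 14 | 27.2% | 14.3% |

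Imbalance is plausible. Its frequency depends on a subtype mix that the documents do not give.

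**2. Validity of the planned test.** If treatment has no effect, random allocation makes every split of the 29 outcomes into 14 and 15 equally likely, whatever drives those outcomes. The exact Mann-Whitney test therefore cannot exceed its nominal level because of subtype. Its attainable level at 14 vs 15 is 4.59%. Simulation (40,000 runs per cell) gives 4.5–4.8% at every subtype effect.

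**3. Power, for 9 / 12 / 14 subtype B patients.** The comparison is with the van Elteren test stratified by subtype.

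| A–B difference | Mann-Whitney (%) | van Elteren (%) | Change (points) |
|---|---|---|---|
| 0 | 70.6 / 70.2 / 69.9 | 68.3 / 68.0 / 67.6 | −2.3 / −2.2 / −2.3 |
| 0.3 SD | 69.1 / 69.3 / 69.3 | 67.8 / 68.1 / 67.8 | −1.3 / −1.2 / −1.5 |
| 0.5 SD | 67.7 / 67.3 / 67.4 | 67.9 / 67.6 / 67.9 | +0.2 / +0.3 / +0.5 |
| 1.0 SD | 61.9 / 59.6 / 59.4 | 68.3 / 67.7 / 67.4 | +6.4 / +8.1 / +8.0 |

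A separate simulation (4,000 runs, treatment effect 1.05 SD, 30% or 50% subtype B) shows the same pattern: with no A–B difference the stratified test loses 3–4 points (75.5% to 72.1%; 75.8% to 72.0%), and at 1.0 SD it gains 5–6 (67.2% to 72.4%; 66.4% to 72.2%).

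**4. Precision.** Mean 95% CI half-width for the mean difference, unadjusted vs adjusted for subtype in a linear model: 0.76 vs 0.77 SD with no A–B difference, 0.78 vs 0.77 at 0.5 SD, and 0.83–0.85 vs 0.77 at 1.0 SD. Adjustment does not bring the half-width below about 0.77 SD. That width comes from having 29 patients.

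**5. Size of the distortion when imbalance occurs.** Shift in the arm difference = gap × A–B difference. Among allocations with a gap of at least 20 points, the mean gap is 29–31 points (9–14 subtype B patients).

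- At 0.5 SD the shift is about 0.30 × 0.5 = 0.15 SD. The standard error is √(1/14 + 1/15) = 0.37 SD, so the shift is about 0.4 of a standard error.
- The Mann-Whitney false-positive rate within those allocations is about 5% with no A–B difference, 6% at 0.5 SD and 8–9% at 1.0 SD.

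**The case for a change.** The strongest counter-argument is conditional. Only one allocation took place, so validity averaged over all allocations is little comfort if that one was unbalanced. With a 1.0 SD A–B difference, the Mann-Whitney false-positive rate is 8–9% among allocations with a gap of at least 20 points, and about 10–11% at 30 points or more, while adjusted tests stay near 5%. Moreover, a linear model with subtype as covariate shows no loss in the simulations even when subtype is irrelevant (about 72% power against 70% for Mann-Whitney), and the Mann-Whitney test would be kept anyway.

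The arithmetic stands, but it does not establish a fault:

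- The larger figures all need a 1.0 SD A–B difference, as large as the assumed treatment effect. Nothing in the documents supports it. The protocol's remark on poor conservative results concerns subtype C, and excluding C removes the one subtype that the protocol itself singles out.
- The linear model's edge at zero subtype effect is not a gain from adjustment, since there is then nothing to adjust for and its interval is slightly wider (0.77 vs 0.76 SD). It reflects simulated outcomes that are normal, together with a rank test run at an attainable level of 4.59%. The SAP names Mann-Whitney for asymmetric outcomes, where that edge cannot be assumed.
- Both documents are written in the past tense and the protocol already reports the enrolled patients. Stratified allocation is no longer possible, and an adjustment added after outcomes are known would be a post hoc sensitivity analysis.

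It is true that readers would want type and subtype shown by arm. That is routine baseline reporting, and its absence from a short statistics paragraph does not make the planned comparison wrong.

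**Conclusion.** The concern does not hold. An unadjusted two-group rank test after unstratified randomisation is a legitimate analysis, and it keeps its 5% level whatever the subtype effect. Stratifying by subtype is a trade-off: about 2 points of power lost if A and B have the same prognosis (3–4 in the second simulation), no material change at 0.5 SD, and 6–8 points gained at 1.0 SD. The documents do not place this trial on the favourable side of that trade-off, and reasonable statisticians could decide either way with 29 patients. Nor would adjustment rescue the title's claim of equal effectiveness. With arms of 14 and 15, the difference detectable with 80% power is (1.960 + 0.842) × 0.372 ≈ 1.04 SD, a limit set by sample size.

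These figures rest on the assumed 14/15 split, 9–14 subtype B patients, normal outcomes and the stated effect sizes. The conclusion on validity rests only on the allocation having been random. Evidence that A and B differ by clearly more than 0.5 SD would make adjustment worthwhile; the documents contain none.
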